4.6.7.1 Derivation or calculation of outcome variables

The tumour tissue study will be retrospective and hypothesis-generating. Accordingly no calculation of the sample size is feasible. The main study aim will be the evaluation of the interaction between the tumour biological phenotype (ie. HER pathway activated or inactivated) and fulvestrant clinical activity. The latter will be evaluated separately in the two treatment cohorts receiving either 250 or 500 mg of the study drug.

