1.2.1 Rationale for the translational research study on tumour tissue samples

In previous studies it has been shown that the HER family receptor signalling pathway cross-communicates with the oestrogen receptor pathway and regulates the ligand-independent activity of the oestrogen receptor (Gruber CJ et al 2002; Pietras RJ et al 1995). In hormone receptor positive HER-2 positive breast cancer cells, tamoxifen works as an agonist and promotes tumour growth. Early clinical data seem to support these pre-clinical findings (Osborne CK et al 2003).

Recently reported pre-clinical data suggest that oestrogen-dependent cell lines carrying HER-2 over-expression retain a significant level of sensitivity to fulvestrant, although the use of trastuzumab (anti-HER-2 monoclonal antibody) in combination with fulvestrant elicits a more profound and durable antitumour effect on the same breast cancer cell lines (Pietras RJ et al 2003).

These pre-clinical and early clinical data support the following hypotheses that will be explored in the context of the present study :

- Fulvestrant might be more active in tumours carrying a “non-activated” HER-pathway. In tumours carrying the HER pathway activation the combination of fulvestrant with anti-HER pathway compounds might be investigated in future studies.
- The 500 mg fulvestrant dose might be more effective than the 250 mg dose only in the cohort of tumours carrying the HER pathway activation.

To explore these hypotheses, archival tumour samples from patients participating in the clinical trial will be collected and molecular markers belonging to the HER pathway (i.e. membrane receptors, phosphorylated receptors, down stream effectors) will be evaluated using different techniques such as immunohistochemistry, fluorescence in-situ hybridisation, and PCR. In addition, a centralised testing for ER, PgR and Ki-67 will be performed.

Tumour samples will be collected only for those patients who have given their written informed consent. Details regarding the logistics of tumour samples collection are reported in Section 4.10.

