4.6.7 Translational research analyses

In patients with available tumour samples from either the primary tumour or a metastatic site (in the latter case the sample will have been obtained before treatment with the study drug), a molecular marker research will be carried out provided that the patient has given her written informed consent. The main aim of this sub-study will be the identification of a patient cohort which might derive the largest benefit from the use of the 500 mg dose of fulvestrant. In this context the evaluation of a panel of molecular markers involved in the HER pathway seems to be of interest because of the cross-talks existing between the ER and the HER pathway.

HER family receptors (EGF-R, HER-2, HER-3, HER-4), phosphorylated receptors, and downstream effectors such as pMAP Kinase and pAKT will be evaluated. In addition ER, PgR and Ki-67 will also be tested. The tumour samples will not be used for genetic testing.

Since this is a complex area of investigation, which is rapidly evolving and as yet not completely understood, data obtained in this study will not be definitive but potentially can be used in hypothesis generation.

Any data obtained from analysis of tumour tissue will be used for research only, and patient confidentiality will be preserved internally and in any presentations or publications. The samples will be available to scientists either within AstraZeneca or at laboratories/research

institutes contracted to AstraZeneca and/or the translational research coordinating centre and patient confidentiality will be preserved. Each patient will have a unique identifier called the patient E-code. A master list is retained at each centre linking initials to patient E-code.

It is not proposed that the analysis of results from a specific patient are made available routinely to either the subject of the treating physician, however, group results from this study will be published. The patient will be informed of this in the patient information sheet.

Samples will be retained for 10 years and data for 15 years in line with AstraZeneca's current policy.

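### For its dose hypothesis, the HER sub-study plans evaluation within each dose arm but no 500 v 250 mg comparison within HER groups

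*Protocol*

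**What the plan says.** Protocol 1.2.1 gives two hypotheses for the tumour-tissue study. The first does not involve dose: "Fulvestrant might be more active in tumours carrying a" non-activated HER pathway. The second is a comparison between doses: the 500 mg dose "might be more effective than the 250 mg dose only in the cohort of tumours carrying the HER pathway activation".

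The aim is then stated in more than one way:

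- Section 4.6.7 gives as main aim the "identification of a patient cohort which might derive the largest benefit from the use of the 500 mg dose of fulvestrant". This is a between-dose question.
- Section 4.6.7.1 gives as main aim the "evaluation of the interaction between the tumour biological phenotype (ie. HER pathway activated or inactivated) and fulvestrant clinical activity". Dose is not part of it.
- The Synopsis and Section 3.1 speak of how HER activation relates to response to fulvestrant, again without dose.

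On method, 4.6.7.1 says of clinical activity: "The latter will be evaluated separately in the two treatment cohorts receiving either 250 or 500 mg of the study drug". It also says "The tumour tissue study will be retrospective and hypothesis-generating" and "Accordingly no calculation of the sample size is feasible". No section states a joint analysis of the two arms, a dose-by-HER term, or a comparison of 500 mg with 250 mg among HER-activated or among non-activated tumours.

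**The concern.** Evaluating HER status separately in each arm compares activated with non-activated tumours among patients on the same dose. The second hypothesis and the aim in 4.6.7 need the other contrast: 500 mg against 250 mg within each HER group, and how far those two contrasts differ. The method that the protocol fixes therefore matches one of its stated questions and not the other.

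If nothing more is done, the dose hypothesis can only be judged by setting the two arms next to each other. A marker that is clearly associated with outcome in one arm and not in the other invites the conclusion that the dose effect depends on HER status. That pattern arises easily by chance when the marker has the same prognostic effect at both doses. At stake is how the sub-study's group results, which Section 4.6.7 says will be published, are read on the dose question.

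**Working it through.** **1. Main-trial figure, for context.** The sub-study has no sample-size figure of its own. Section 6.5 gives 632 events for HR 0.8, two-sided 5%, 80% power, 1:1. Schoenfeld: 4(1.960 + 0.842)² / (ln 0.8)² = 631; Freedman gives 636. The figure reproduces.

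**2. What within-arm results contain.** Let M500 and M250 be the marker hazard ratios (activated v not) within each arm, and D+ and D− the 500 v 250 mg hazard ratios in activated and non-activated tumours. Then

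ln M500 − ln M250 = ln D+ − ln D−.

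So the two marker hazard ratios, with their standard errors, contain the interaction. They do not contain D+ and D− themselves. For example, M250 = 1.25 and M500 = 1.00 give a ratio of 0.80. This fits D+ = 0.80 with D− = 1.00 (500 mg better only in activated tumours) and equally D+ = 1.00 with D− = 1.25 (no gain in activated, harm in the others). The second hypothesis concerns D+ and D−.

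**3. Side-by-side reading when there is no interaction.** Assumptions, none of them in the protocol: tissue covers half of the 632 events (316, so 158 per arm), marker split 50:50, same marker hazard ratio in both arms. The standard error of the log marker hazard ratio per arm is 2/√158 = 0.159.

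- HR 1.3: power per arm = Φ(0.262/0.159 − 1.96) = 0.378; significant in exactly one arm = 2 × 0.378 × 0.622 = 0.47.
- HR 1.5: power per arm = Φ(0.405/0.159 − 1.96) = 0.722; significant in exactly one arm = 2 × 0.722 × 0.278 = 0.40.

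Varying the assumed tissue coverage, with marker prevalence 20–50%:

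| Events with tissue | Marker HR 1.3 | Marker HR 1.5 |
|---|---|---|
| 632 | 46–50% | 10–29% |
| 316 | 39–47% | 40–50% |
| 200 | 30–38% | 47–50% |

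**4. Comparison with a joint test.** Simulation with 4,000 trials per setting, 360 uncensored exponential times and 30% prevalence:

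| Setting | Significant in exactly one arm | Interaction test rejects |
|---|---|---|
| No interaction (dose HR 0.8 in both groups), marker HR 1.3 | 47% | 5% |
| No interaction (dose HR 0.8 in both groups), marker HR 1.5 | 42% | 6% |
| True interaction (dose HR 0.6 activated, 1.0 otherwise) | 45% | 59% |

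The one-arm-only pattern is about as frequent with this interaction as without it. The third setting is one chosen case, in which the marker hazard ratio is 1.29 at 250 mg and 1.29 × 0.6 = 0.77 at 500 mg.

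**5. What a joint analysis could show.** The variance of the log interaction is 4/(E·p) + 4/(E·(1 − p)), with E events and prevalence p. For E = 316 and p = 0.5 it is 4/158 + 4/158 = 0.0506, so the standard error is 0.225. The 95% interval for the ratio of hazard ratios is the estimate divided and multiplied by exp(1.96 × 0.225) = 1.55. The interval for the dose effect within one HER group uses exp(1.96 × 0.159) = 1.37. If D+ = 0.8 and D− = 1.0, with prevalence 20–50%, interaction power is 20–29% with 632 events, 12–17% with 316 and 9–12% with 200. Power of 80% would need about 2,500 to 3,900 events.

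**The case against.** The sentence in 4.6.7.1 stands under a heading on deriving outcome variables and names no model, test or decision rule. A reader might infer that the plan will declare a dose-specific marker effect when the marker is significant in one arm only. Nothing in the protocol says so, and the percentages above describe how often that pattern occurs, not an error rate of the plan.

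A reader might also infer that the by-arm analysis makes the dose-by-HER question untestable. That goes too far. The arms are independent, so the two within-arm log hazard ratios and their variances yield the interaction, as step 2 shows. If activity were tabulated by HER group in each arm, the four cells could also be compared by dose. What stands is that the protocol plans neither step.

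The by-arm evaluation is not misplaced for everything. It bears on the first hypothesis and on the correlation aim in the Synopsis and Section 3.1, although without an untreated group it cannot separate prognosis from drug activity. The remark in 1.2.1 on future combination studies belongs to that first hypothesis, so it should not be counted as a consequence of leaving the dose question unaddressed.

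Finally, detail may lie in a separate plan: the sub-study is analysed at its coordinating centre (4.10) and reported apart from the trial report (5.1). That would excuse a missing model specification. It does not remove the mismatch between a stated question and the method that is stated. Low power is a fair objection to a confirmatory test, but not to an estimate with its interval.

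**Conclusion.** The point holds in limited form. For the second hypothesis in 1.2.1 and the aim in 4.6.7, the analysis stated in 4.6.7.1 gives no 500 v 250 mg comparison within HER groups and no direct estimate of the interaction. For the first hypothesis it is a usable descriptive analysis.

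The size of the risk depends on assumptions. About 40–47% of trials would show the one-arm-only pattern without any interaction at 158 events per arm and a 50:50 marker. Across the wider assumed ranges this runs from 10% to 50%. Tissue coverage, marker prevalence, marker effect and TTP as the outcome are all assumed here; the protocol gives none of them for the sub-study.

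Severity is low. The sub-study is optional, retrospective and hypothesis-generating, and the TTP, survival and safety conclusions do not depend on it.

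**What to change.** Keep the within-arm associations in 4.6.7.1 as descriptive results for the first hypothesis, and add for the second:

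*Both dose arms will be analysed together, with terms for dose, HER status and dose by HER status (Cox model for TTP, or logistic model for response). The effect of 500 mg relative to 250 mg will be reported with its 95% confidence interval in HER-activated and in non-activated tumours, together with the interaction estimate and its 95% confidence interval. These are exploratory estimates. The dose hypothesis will not be judged by comparing the significance of the marker between arms.*

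The aims in the Synopsis and Sections 3.1, 4.6.7 and 4.6.7.1 should be aligned at the same time, so that each hypothesis has a named analysis.

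The change needs no new patients, samples or measurements. Its cost is that the intervals will be wide, with factors of about 1.4 within an HER group and 1.55 for the interaction under the assumptions above. Such width is acceptable for a study meant to generate hypotheses.

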4.7 Safety measurements and variables

The methods for collecting safety data are described below.

4.7.1 Adverse events

4.7.1.1 Definitions

The definitions of adverse events (AEs), serious adverse events (SAEs) and other significant adverse events (OAEs) are given below. It is of the utmost importance that all staff involved in the study are familiar with the content of this section. The principal investigator is responsible for ensuring this.

Adverse event

An adverse event is the development of an undesirable medical condition or the deterioration of a pre-existing medical condition following or during exposure to a pharmaceutical product, whether or not considered causally related to the product. An undesirable medical condition can be symptoms (e.g., nausea, chest pain), signs (e.g., tachycardia, enlarged liver) or the abnormal results of an investigation (e.g., laboratory findings, electrocardiogram). In clinical studies, an AE can include an undesirable medical condition occurring at any time, including run-in or washout periods, even if no study treatment has been administered. **Any events that are unequivocally because of progression of disease must not be reported as an AE. Adverse events of bone pain (ie not related to disease progression) should be reported as an adverse event.**

Serious adverse event

A serious adverse event is an AE occurring during any study phase (i.e., run-in, treatment, washout, follow-up), and at any dose of the investigational product, comparator or placebo, that fulfils one or more of the following criteria:

- results in death
- is immediately life-threatening
- requires in-patient hospitalisation or prolongation of existing hospitalisation
- results in persistent or significant disability or incapacity
- is a congenital abnormality or birth defect
- is an important medical event that may jeopardize the patient or may require medical intervention to prevent one of the outcomes listed above.

The causality of SAEs (ie, their relationship to study treatment) will be assessed by the investigator(s), who in completing the relevant case report form must answer “yes” or “no” to the question “Do you consider that there is a reasonable possibility that the event may have been caused by any of the following – study medication – other medication?” For further guidance on the definition of a SAE and a guide to the interpretation of the causality question, see Appendix B to the Clinical Study Protocol. **Any serious events that are unequivocally because of progression of disease must not be reported as an SAE.**

Note that SAEs that could be associated with any study procedure should also be reported. For such events the causal relationship is implied as “yes”.

Other Significant Adverse Events (OAE)

OAEs will be identified by the Drug Safety Physician and if applicable also by the Clinical Study Team Physician during the evaluation of safety data for the Clinical Study Report. Significant adverse events of particular clinical importance, other than SAEs and those AEs leading to discontinuation of the patient from study treatment, will be classified as OAEs. Examples of these are marked haematological and other laboratory abnormalities, and certain events that lead to intervention (other than those already classified as serious), dose reduction or significant additional treatment. For each OAE, a narrative may be written and included in the Clinical Study Report.

4.7.1.2 Recording of adverse events

Any detrimental change in a patient's condition subsequent to their entering the study should be considered an AE.

(i) Method of detecting AE/SAEs

At each visit the method of detecting AEs and SAEs will be by:

- (a) information volunteered by the patient or carer
- (b) open-ended and non-leading verbal questioning of the patient at every visit such as the following: *How are you feeling? Have you had any (other) medical problems since your last visit?*
- (c) observation by the investigational team, other care providers or relatives

(ii) Time period for collection of AEs/SAEs

Non-serious adverse events and SAEs will be collected from the time consent is given, throughout the treatment period and up to 8 weeks after the last injection of study medication. During the survival follow up phase only SAEs for patients still on study treatment (and up to 8 weeks after the last injection of study medication), will be recorded and reported to Quintiles who will inform the appropriate AstraZeneca Patient Safety Department. These should be reported within the timelines stated in Section 4.7.1.3 in the Clinical Study Protocol.

(iii) Collection of AE data

All AEs will be recorded on the CRFs provided. A description of the event, including its date of onset and resolution, whether it constitutes a SAE or not, any action taken (e.g., changes to study treatment, other treatment given, and follow-up tests) and outcome, should be provided along with the investigator's assessment of causality (the relationship to the study treatment). AEs will also be graded according to the NCI CTC version 3.

(iv) Causality

For an AE to be a suspected drug-related event, there should be at least a reasonable possibility of a causal relationship between the study medicinal product and the AE (see Appendix B for guidelines on interpretation of causality).

(v) Intensity

It is important to distinguish between serious and severe AEs. Severity is a measure of intensity whereas seriousness is defined by the criteria in Section 4.7.1.1. An AE of severe intensity need not necessarily be considered serious. For instance nausea that persists for several hours may be considered severe nausea, but not an SAE. On the other hand, a stroke that results in only a limited degree of disability may be considered a mild stroke but would be an SAE. The following definitions will be used in this study:

- mild (awareness of sign or symptom, but easily tolerated)
- moderate (discomfort sufficient to cause interference with normal activities)
- severe (incapacitating, with inability to perform normal activities)

The degree of severity will also be recorded by means of the National Cancer Institute, Common Toxicity Criteria (CTC) criteria (version 3) for all events with an assigned CTC grade.

(vi) Disease progression

Where there is deterioration in the condition for which the study treatment is being used, there may be uncertainty as to whether this is lack of efficacy or constitutes an AE. In such cases, unless the AstraZeneca or reporting physician considers that the study treatment contributed to the deterioration, or local regulations state to the contrary, the deterioration should be considered to be disease progression and not an AE. Expected progression and signs and symptoms of the disease/disorder being studied, unless more severe in intensity or more frequent than expected for the patient's condition, should not be reported as an AE or SAE, but documented elsewhere in the CRF.

Any events that are unequivocally due to progression of disease must **not** be reported as an AE.

(vii) Adverse events related to elective surgery and surgery for breast cancer

A hospitalisation for elective surgery or surgery for breast cancer should not be recorded as an adverse event or as a serious adverse event. However, complications of surgery should be recorded as adverse events or as serious adverse events if they fulfil any of the criteria for seriousness (see Section 4.7.1.1).

(viii) Deaths

All deaths that occur during the study, or within the protocol defined follow-up period after the last injection of study treatment, must be reported as follows:

Death, clearly the result of disease progression should be reported to the study monitor at the next monitoring visit and should be documented in the CRF, but should not be reported as an SAE.

Where death is not due (or not clearly due) to progression of the disease under study, the AE causing the death must be reported to the study monitor as an SAE within 24 hours. The report should contain a comment regarding the co-involvement of progression of disease, if appropriate, and should assign main and contributory causes of death.

(ix) New Cancers

The development of a new cancer should be regarded as an AE. New cancers are those that are not the primary reason for the administration of the study treatment and have been identified after the patient's inclusion in this study. They do not include metastases of the original cancer. Symptoms of metastasis or the metastasis itself should not be reported as an AE/SAE as they are considered to be disease progression.

(x) Abnormal laboratory values/vital signs

The reporting of laboratory /vital signs abnormalities as both laboratory findings and adverse events should be avoided. They should not be reported unless any criterion for a SAE is fulfilled, the laboratory /vital signs abnormalities causes the patient to discontinue from the study, or the investigator insists the abnormality should be reported as an AE. If an abnormal laboratory value /vital sign is associated with clinical signs and symptoms, the sign/symptom should be reported as an AE and the associated laboratory result/vital sign should be considered additional information that must be collected on the relevant CRF.

(xi) Pregnancy

Only postmenopausal women are eligible to participate in this study (see Section 9.4.). However, if for any reason a pregnancy occurs it should be reported to AstraZeneca immediately using specific pregnancy reporting forms.

(xii) Overdose

An overdose is defined as a dose administered to a subject that is in excess of the randomised dose for that patient.

Should an overdose (accidental or deliberate) occur, it must be reported in accordance with the procedures described in Section 9.3. All symptoms associated with the overdose should be reported as AEs.

AEs that occur in association with an overdose should be reported in the same manner as other AEs, following the procedures described in the protocol.

Please refer to Section 9.3.

(xiii) Follow up of AEs/SAEs

After the initial AE/SAE report, the investigator is required to follow up proactively each patient and provide further information to AstraZeneca on the patient's condition. During the study all AEs/SAEs should be followed up to resolution, or until the condition stabilizes, unless the event is considered by the investigator to be unlikely to resolve due to the patient's underlying disease, or the patient is lost to follow up.

(xiv) Handling unresolved AE/SAEs at completion/withdrawal

Any SAEs that are ongoing when the patient completes the study, or at patient discontinuation from the study, must be followed until resolution or until the patient is lost to follow up, unless, in the investigator's opinion, the condition is unlikely to resolve due to the patient's underlying disease.

AstraZeneca reserves the right to ask for further information on any AE, which may be considered of interest.

(xv) Interactions

Current experience with fulvestrant has not shown potential for drug interaction.

However, for the purpose of this study if, in the opinion of the investigator, an interaction between fulvestrant and a concomitant drug or between concurrent drugs has occurred, this should be reported as an adverse event. Information should be provided as to which drugs the interaction has occurred between. Any adverse event that occurs as a consequence of the interaction and fulfils the criteria for seriousness must be reported to AstraZeneca immediately, on the same day as per other serious adverse events. Adverse events (serious and non serious) arising as the result of an interaction should be recorded on an adverse event form with an indication that the event is a result of an interaction. For example 'hypotension related to drug-drug interaction'.

(xvi) Review of safety data by the Independent Data Monitoring Committee (IDMC)

The procedures for the review of safety data by the IDMC are described in Appendix D.

